For example, a subset of calls (approximately 20 calls with and 20 calls without a birth outcome of interest) will be evaluated by the call center manager as a quality control and monitoring procedure. A similar number of CATI calls adequate to ensure validity will be sent to the FIDA app to be checked by CATI remote home visits within 42 days of delivery for each of the cases. These will be done as soon as possible after the CATI closes the case and within 7 days. The FIDA will visit the home and pass their mobile phone with a CATI on the line to conduct the outcomes interview. When cell service is unavailable, the FIDA will conduct the outcomes interview.

Regular assessment of FADA skills (confirming they achieve 100% concordance on a sample of three observations) will be conducted. FADAs Team Leaders will also re-enter a sample of paper forms into the mobile device for comparison.

An integrated quality control and monitoring (QCM) framework will support data quality management. The overall framework will be to monitor data collection activities and control the quality of data with respect to its completeness and accuracy.

The three most critical activities involved in the data collection process, which will be monitored closely, are FIDA facility visits, follow-up after 7 days by the call center, and call center validation visits by FIDA. We will monitor the completeness and accuracy of data describing birth registration, health outcomes at discharge, and health outcomes post delivery within 7 days as described above. Double data entry will be performed on a subset of the data for benchmarking and quality control as described above.

Data safety monitoring board

A data safety monitoring board (DSMB) will be established to oversee the safety and scientific accuracy of the study. The DSMB will contain a minimum of three members external to the study team, of which:

- At least two of the members will be maternal-child health experts, preferably an obstetrician-gynecologist and a pediatrician.
- One of the members will be a senior statistician
- One of the DSMB members will be designated as the DSMB Chairperson.
- None of the members will be directly involved in the conduct of the study.

The DSMB will review the study design and protocol, including the data collection protocols and processes. It will also review outcomes data at intervals of 6 months, at the interim point at the end of phase II, and final analyses. The DSMB will advise and decide on the continuation, early stoppage, and/or final termination of the trial based on this periodic data review.

4.9. Are there any anticipated circumstances under which participants will be withdrawn from the research without their consent?

No Yes: If yes; describe the circumstances as well any associated procedures to ensure orderly termination

5. Data/Statistical Analyses Plan

5.1. Briefly describe the plan for data analysis (including the statistical method if applicable)

Interim analysis and early stopping

The trial will be monitored by the DSMB for possible early stopping, if a large intervention effect occurs at the time of interim analysis, using a Haybittle–Peto approach.[33] Specifically, an interim Rao-Scott chi-square test will be performed after approximately 25% (45,000) of the total births are enrolled, which should occur approximately 15 months after the trial phase begins (Phase 2 data collection complete). In order to stop the study at this point in favor of the SCC program, the P-value for this Rao-Scott chi-square test must be ≤ 0.001 . The stopping rule for this study will be used as a guideline rather than as a hard-and-fast rule. Any final decision will also consider additional endpoints such as differences in complications, process measures, birth attendant compliance to the checklist, as well as an estimate of the intervention effect adjusted for birth attendant's compliance to the checklist. If the findings of the interim analysis are in favor of stopping the trial due to beneficial effect of the SCC program on the combined measure of maternal and newborn outcomes, the research study will be stopped. For ethical reasons, the

promised implementation support for enrolled sites would continue for the originally planned duration of the trial.

Final analysis

If the study is not stopped, the final analysis will be performed when approximately 86,000 birth events have been accrued in each arm. Using the Haybittle–Peto approach, the P-value for this Rao-Scott chi-square test must be ≤ 0.05 for the intervention and comparison groups to be declared significantly different. The final analysis is expected to occur up to 35 months after the start of the trial phase.

Secondary analyses

Secondary analyses will use the Rao-Scott chi-square test, adjusted for matching and clustering, to compare groups with respect to selected individual health outcomes and process measures. Since these are secondary analyses, no formal stopping rules will be applied and all tests will be performed at a 5% type I error rate. The following power calculations again assume an intracluster correlation of 0.075 (being conservative here, we use the maximum ICC for newborn outcomes in the 2005 WHO Global Survey on Maternal and Perinatal Health).

The secondary maternal, fetal, and newborn health outcomes will be measured on the entire sample. For a given outcome the Rao-Scott chi-square test statistic will have greater than 80% power (with a 5% Type I error) to detect a minimum absolute difference in rates between the comparison and SCC groups of 7 per 100 if there is no effect of matching ($Deff_M=1$) and 5 per 100 at the most conservative design effect for matching ($Deff_M=0.55$). We note that 5 per 100 is the estimated absolute difference that can be detected without a priori knowledge of the rate in the comparison group, and is estimated assuming that the rate in the comparison group is 50 per 100 (50%); as the comparison group rate gets further from 50%, we can detect a smaller difference between the comparison and SCC groups.

Structured observation of health worker performance will be performed on a subsample of births: an estimate of 7800 births at each of three pause points (1 observation point for the first 2 pause points, 2 observation points for pause point 3) will be observed from 15 matched-pairs of facilities (30 facilities). Thus, we will sample 25% of the total facilities in the study (30 facilities) to observe processes. For a given process measure outcome at 8 weeks of coaching with an $ICC=0.01$ and $Deff_M=1$ (both most conservative), which will be measured on a sample of 1,800 births (average of 60 births per facility), the Rao-Scott chi-square test statistic will have greater than 80% power (with a 5% Type I error) to detect a minimum difference in rates between the comparison and SCC groups of 8.5 per 100. We note again that 8.5 per 100 is the estimated difference that can be detected without any a priori knowledge of the rate in the comparison group, and is thus estimated assuming that the rate in the comparison group is 50 per 100 (50%); as the comparison group rate gets further from 50%, we can detect a smaller difference between the comparison and SCC groups. Further, based on the results from the SCC program pilot study in Karnataka, we expect to see much larger differences than 8.5 per 100 between the comparison and SCC groups.

We will also do an initial analysis on pre intervention observation (60 at each observation point per facility) and early post intervention (starting 8 weeks after intervention) to qualitatively explore that change is starting, before additional facilities are initiated but no statistical analysis are planned. If no change is seen, then the intervention component will be intensified as the additional 13 pairs are enrolled for the phase II.

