- D. **Rates of adherence by health workers to essential childbirth practices (“process measures”):** Specifically, the rates of completion of the following practices will be assessed in a sample of approximately 7800 deliveries for each of pause-points 1, 2, and 3: including maternal temperature obtained on admission, maternal blood pressure obtained on admission, partograph use, inappropriate initiation of oxytocin before delivery of the baby, appropriate hand hygiene (use of soap and water, and wearing clean gloves) by health workers at the time of delivery, skin-to-skin care, oxytocin administration within 1 minute after birth, newborn weight and temperature obtained within 1 hour after birth, and initiation of breastfeeding within 1 hour after birth.

Additional outcomes

Additional outcomes to be evaluated are:

- A. Rate of SCC use.
- B. Impact of the SCC program on the availability of the essential resources including: partograph, oxytocin, antibiotics, Magnesium Sulphate, gloves, water, and soap.
- C. Operational changes in workflow introduced independently by the facility staff, induced by the SCC program.
- D. Impact of the SCC program on the rates of medication administration; specifically oxytocin, antibiotics for mother, Magnesium Sulphate, antibiotics for baby, antiretroviral for mother, and antiretroviral for baby.

- E. Qualitative user impressions of checklist use and facility culture as assessed by survey of health workers.
- F. Patient satisfaction as assessed by survey of patients.

3. Study Setting

3.1. Identify the sites or locations where the research will be conducted.

This trial will be conducted in a single state (Uttar Pradesh; UP) in a single country (India). The maternal mortality ratio in UP is 359/100,000 live births.[19] Maternal near-miss data for UP are not available, but estimates from similar low-income settings in Indonesia, Syria, and Latin America range from 14-34/1,000 live births. [20–22] The intrapartum-related (fresh) stillbirth rate in UP is 27.7/1,000 births and the rate of neonatal death on the first day of life is 11/1,000 live births.

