5.2. Is there a sample size/power calculation?

No Yes: If yes; describe the calculation and the scientific rationale, and, if applicable, by site and key characteristics such as participant demographics

Intracluster correlation

The nature of the SCC program as a health system innovation precludes its randomization at the level of individual patients and instead incorporates a cluster design (i.e., randomization at the facility, or cluster, level). Estimating intracluster correlation coefficients (ICCs) is necessarily based on extrapolations from prior studies. ICC estimates have been derived for maternal and newborn health from the 2005 WHO Global Survey on Maternal and Perinatal Health (analyzing data from more than 90,000 pregnancies and births taking place in 120 hospitals in 8 Latin American countries). [22] For maternal and newborn outcome variables in this setting, the overall median ICCs were 0.011 (interquartile range 0.007–0.037) and 0.054 (interquartile range 0.013–0.075), respectively. Measures specific to this trial’s causal effect for which an ICC was estimated include neonatal death at 7 days (ICC=0.005) and maternal death (ICC=0.0003). The population studied and that in north India are not identical; clinical care delivered in Latin America may be of higher quality than that in UP; the implication is that ICCs may be lower in Latin America. For additional reference, numerous studies evaluating neonatal death in village settings in India and elsewhere in Asia use much lower ICCs, ranging from 0.0005 to 0.006. Considering these available data, and following discussion with biostatistics experts, including a reviewer at The Bill and Melinda Gates Foundation (BMGF), we therefore assume for this study the relatively conservative ICC estimate of ICC=0.01.

Cluster size and number

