than 100/1,000. The baseline rate used in this study will be 60/1,000; this is purposively set lower than the baseline data to (1) maintain conservatism since the preliminary data is based on a small sample and we do not want to risk under powering the study; and (2) to facilitate the possibility of demonstrating significant changes in sub-analyses (i.e., perinatal death rate).

Estimated event rate reduction

Based on knowledge of the relatively poor existing quality of healthcare services in UP, and the results of the SCC program pilot study which demonstrated marked improvement in health worker performance, we feel that achieving up to a 15% reduction in prior outcomes with the SCC program is feasible in this population and, at the same time, will enable the calculation of a practical sample size.

Statistical power

The Rao-Scott chi-square test statistic, which adjusts for the matched-pair cluster randomization scheme, will be used to compare the rates of the primary outcomes in the comparison and intervention groups. For our matched cluster randomized design, the necessary sample size per treatment group, N , using the Rao-Scott chi-square test statistic, can be written as a product of three terms:

$N = n \times Deff_C \times Deff_M$, where

n = sample size per treatment group for a simple random sample of independent patients

$Deff_C$ = Design effect 'for an unmatched cluster randomized design versus a simple random sample, $= 1 + (m-1) \times ICC$, with

m = average number of patients in a cluster (birth facility) ≈ 1440 patients

ICC = intra-cluster (birth facility) correlation coefficient $\approx .01$

$Deff_M$ = Design effect 'for a matched versus unmatched cluster randomized design

In this study, with $ICC=0.01$, we approximate $Deff_C = 15.4$, so that within-facility clustering has a significant impact. The best available estimate for $Deff_M$ when using our matching algorithm can be obtained from our team member's matched cluster randomized design in Mexico.[41, 47] In the Mexico study (in which 14 outcomes were measured), $Deff_M$ was at most 0.55 (resulting in at least a 45% reduction in the total sample size); 10 outcomes had a $Deff_M$ of 0.2 or smaller (giving at least an 80% reduction in the total sample size); and 7 outcomes had a $Deff_M$ of 0.1 or smaller.

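### The secondary-outcome power statement is slightly wrong: 5 per 100 at a matching effect of 0.55 has about 77% power, not over 80%, and its ICC of 0.075 is misdescribed

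*Combined protocol and SAP*

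**What the plan says.** Section 5.1, Secondary analyses, says that for a given secondary outcome "the Rao-Scott chi-square test statistic will have greater than 80% power (with a 5% Type I error) to detect a minimum absolute difference" of "7 per 100 if there is no effect of matching" (Deff_M = 1), or of "5 per 100 at the most conservative design effect for matching" (Deff_M = 0.55). It says "all tests will be performed at a 5% type I error rate".

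The inputs are introduced with "The following power calculations again assume an intracluster correlation of 0.075". The text calls this value conservative and identifies it as the largest ICC for newborn outcomes in the WHO survey. It discloses that 50% is used because the comparison rate is not known in advance, and that smaller differences are detectable at rates further from 50%.

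Section 5.2 (Intracluster correlation) describes the same survey: "For maternal and newborn outcome variables in this setting, the overall median ICCs were 0.011" (interquartile range 0.007 to 0.037) for maternal variables, and 0.054 (interquartile range 0.013 to 0.075) for newborn variables. It gives outcome-specific ICCs of 0.005 for neonatal death at 7 days and 0.0003 for maternal death, and adopts 0.01 for the trial.

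**The concern.** Three things do not fit.

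- The power for 5 per 100 falls below the stated 80% when the plan's own formula is applied to the paragraph's own inputs.
- The description of the ICC conflicts with section 5.2 twice: on what the primary calculation assumed, and on where 0.075 sits in the survey distribution.
- The differences quoted are larger than the whole rate of the mortality outcomes for which section 3.1 gives figures. It puts maternal mortality at 359 per 100,000 live births and says the fresh "stillbirth rate in UP is 27.7/1,000 births and the rate of neonatal death on the first day of life is 11/1,000 live births".

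No design decision depends on this paragraph. What is at stake is whether a reader can learn from it what the trial could detect on its secondary health outcomes.

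**Working it through.** **Inputs.** Births per arm: about 86,000 (5.1, Final analysis). Cluster size m = 1,440, and N = n × Deff_C × Deff_M with Deff_C = 1 + (m − 1) × ICC (5.2, Statistical power). Deff_M = 0.55 or 1, ICC = 0.075 and comparison rate 50% (5.1). The number of sides of the test is not stated; two-sided 5% is assumed and checked in step 1.

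**Step 1: reproduce the primary sample size.** For 6.0% against 5.1%, two-sided 5%, 80% power, the pooled two-proportion formula gives n = 10,158 per arm. Deff_C = 1 + 1,439 × 0.01 = 15.39. Then 10,158 × 15.39 × 0.55 = 85,982 per arm, or 171,964 in all, which is the plan's figure. A one-sided test would give 135,466. So the formula and the two-sided test are the plan's own.

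**Step 2: effective sample size for the secondary statement.** Deff_C = 1 + 1,439 × 0.075 = 108.925.

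- Deff_M = 1: 86,000 / 108.925 = 790 per arm.
- Deff_M = 0.55: 86,000 / (108.925 × 0.55) = 1,436 per arm.

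**Step 3: power.** With p̄ the mean of the two rates, power = Φ{[d√n − 1.96 √(2p̄(1 − p̄))] / √(p1(1 − p1) + p2(1 − p2))}.

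- 50% against 43%, n = 790: (1.967 − 1.96 × 0.7054) / 0.7036 = 0.83, so power is 79.7%. The 80% difference is 7.03 per 100.
- 50% against 45%, n = 1,436: (1.894 − 1.96 × 0.7062) / 0.7053 = 0.72, so power is 76.5%. The 80% difference is 5.22 per 100. At 5.3 per 100 power is 81.2%.

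**Step 4: could another reading give 80% at 5 per 100?** Two-sided normal variants of cluster size, births per arm and direction give 76.4% to 76.9%. A t reference gives about 75% to 76%. With 60 facilities per arm and unlimited births in each, effective n tends to 60 / (0.075 × 0.55) = 1,455 and power to 77.1%. A one-sided test gives about 85%, but its 80% differences are 6.2 and 4.6 per 100, so it does not reproduce the 7, and it contradicts step 1. Exactly 80% at 5 per 100 needs n = 1,565, that is 1,565 × 108.925 × 0.55 ≈ 93,760 births per arm, or about 65 pairs.

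**Step 5: the ICC wording.** The primary calculation in 5.2 uses 0.01, so *again* is wrong. Section 5.2 gives 0.075 as the top of the newborn interquartile range, so a quarter of those variables may lie at or above it, and *maximum* does not match.

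**Step 6: low rates.** A fall of 5 per 100 exceeds 0.36 (maternal death), 2.77 (fresh stillbirth) and 1.1 (first-day neonatal death) per 100. Reductions detectable with 80% power, by the same formula:

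| Cited rate | ICC | Deff_M 0.55 | Deff_M 1 |
|---|---|---|---|
| Maternal death 0.359% | 0.0003 (cited) | 0.68 per 1,000 (19%) | 0.90 per 1,000 (25%) |
| First-day neonatal death 1.1% | 0.005 (cited, for 7-day death) | 2.8 per 1,000 (25%) | 3.7 per 1,000 (33%) |
| Fresh stillbirth 2.77% | 0.01 (assumed, the primary value) | 6.1 per 1,000 (22%) | 8.1 per 1,000 (29%) |

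The planned outcomes are fresh or macerated stillbirth, and death within 7 days. The last two cited rates are therefore lower bounds for those outcomes, and the percentages beside them are upper bounds.

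**The case against.** The strongest reply is that the paragraph gives whole numbers per 100: 7.03 and 5.22 round to the printed 7 and 5. The number of facilities and births comes from the primary composite, not from here. This largely stands and sets the scale of the point. But rounding 5.22 down makes a claim of more than 80% power untrue, by 3.5 percentage points, whereas for 7 the shortfall is only 0.3.

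A reader might go further and infer that the plan claims power it cannot have for rare outcomes. The documents do not support that. The 50% rate is declared as a worst case, and the remark about smaller differences is correct: at 2.77%, ICC 0.075 and Deff_M 0.55, the detectable fall is about 1.5 per 100. The text also speaks of an absolute difference without direction.

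Nor can it be shown that 0.075 and 50% suit none of the secondary outcomes. Only maternal and neonatal death have their own ICCs, and no rates are given for transfer, revisit, transfusion, hysterectomy or C-section. Section 5.2 also says that ICCs may be lower in Latin America than in Uttar Pradesh, which favours a high planning value.

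Finally, the low baseline rate in 5.2 is said "to facilitate the possibility of demonstrating significant changes in sub-analyses (i.e., perinatal death rate"). That names a possibility and states no power, so it does not contradict 5.1.

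**Conclusion.** The point holds as a minor correction. The stated power for 5 per 100 at Deff_M 0.55 is about 77% rather than above 80%, and the difference with 80% power is 5.2 per 100. The 7 per 100 figure can stand. Two descriptions of the ICC of 0.075 conflict with section 5.2. For the rare mortality outcomes the statement is uninformative rather than false.

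This rests on a two-sided test, equal facility sizes and no loss to follow-up. Unequal facility sizes or a t reference would lower power a little further. The low-rate figures also treat the statewide rates in 3.1 as rates per birth event in the trial's facilities.

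**What to change.** In section 5.1, Secondary analyses:

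1. Replace 5 per 100 with 5.3 per 100, or keep 5 and state about 77% power.
2. Delete *again*, and replace *maximum* with *upper quartile*.
3. Preferably, add detectable differences at low rates using the ICCs that 5.2 cites, as in the table above. Label the stillbirth rate as fresh only and the neonatal rate as first day only, so that the relative reductions read as upper bounds. Mark the 0.01 used for stillbirth as an assumption.

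The cost is a short recalculation and a few words. The sample size, design and analysis do not change. The low-rate figures would help the plan: with its cited ICC, maternal death comes out at a 19% to 25% detectable reduction, which the present paragraph does not convey.

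### Section 5.1 sets an ICC of 0.075 for secondary-analysis power, then uses 0.01 for process measures and calls it the most conservative value

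*Combined protocol and SAP*

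**What the plan says.** Section 5.1, under Secondary analyses, opens by saying that the Rao-Scott test will be used "to compare groups with respect to selected individual health outcomes and process measures". Shortly afterwards it states: "The following power calculations again assume an intracluster correlation of 0.075 (being conservative here, we use the maximum ICC for newborn outcomes". It then gives detectable differences for the health outcomes of 7 per 100 without a matching effect and 5 per 100 with a matching design effect (Deff_M) of 0.55.

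Later under the same heading comes the process-measure calculation: "For a given process measure outcome at 8 weeks of coaching with an $ICC=0.01$ and $Deff_M=1$ (both most conservative". It uses 1,800 births, on average 60 in each of 30 facilities, and reports more than 80% power at 5% type I error for a difference of 8.5 per 100, taking a comparison rate of 50%. The paragraph closes by saying "we expect to see much larger differences than 8.5 per 100 between the comparison and SCC groups".

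Section 5.2 (Intracluster correlation) lists the ICCs available to the planners. All are for maternal or newborn outcomes. The maternal median is 0.011 (interquartile range 0.007 to 0.037) and the newborn median is "0.054 (interquartile range 0.013–0.075), respectively". Lower values are also listed: "neonatal death at 7 days (ICC=0.005) and maternal death (ICC=0.0003"), and Asian village studies of neonatal death that "use much lower ICCs, ranging from 0.0005 to 0.006". The section concludes: "we therefore assume for this study the relatively conservative ICC estimate of ICC=0.01".

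**The concern.** One section uses two ICCs that differ by a factor of 7.5 and describes each as conservative. As written, the lead-in with 0.075 covers process measures, yet the process-measure calculation uses 0.01. No reason is given for the change, and no process-measure ICC is cited for either value. Section 5.2 makes the weaker claim that 0.01 is relatively conservative, and several of the values it lists are higher.

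What is at stake is how a reader would interpret a small or null difference in a process measure. The text says that 8.5 per 100 was detectable under the least favourable clustering. If that is not so, a null result would be given more weight than the design supports.

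**Working it through.** **Inputs.** From Section 5.1: 1,800 births, 30 facilities in 15 pairs, so 900 births per arm; m = 60 per facility; comparison rate p1 = 0.50; 5% type I error; 80% power. From Section 5.2 (Statistical power): Deff = [1 + (m − 1) × ICC] × Deff_M. Two-sided testing is my assumption, since the section does not state it.

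**Formula.** Effective births per arm n_e = 900 / Deff. Power = Φ{[d√n_e − 1.96√(2p̄(1 − p̄))] / √(p1(1 − p1) + p2(1 − p2))}, where p2 = p1 − d and p̄ is the mean of p1 and p2. The detectable difference is the d that gives 80% power.

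**The plan's own figure.** At ICC 0.01 and Deff_M 1, Deff = 1 + 59 × 0.01 = 1.59 and n_e = 900 / 1.59 = 566. Power at d = 0.085 is 82.0%, and the detectable difference is 8.3 per 100 (8.5 with a continuity correction). The stated 8.5 reproduces.

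**Is 0.075 really used in that section?** For the health outcomes, take 171,964 / 2 = 85,982 births per arm and m = 171,964 / 120 = 1,433.
- ICC 0.075: Deff_C = 1 + 1,432 × 0.075 = 108.4. The detectable difference is 7.0 per 100 at Deff_M 1 and 5.2 at Deff_M 0.55, against a stated 7 and 5.
- ICC 0.01: Deff_C = 15.32. The differences would be 2.6 and 2.0.

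So 0.075 was used there and is not a misprint.

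**Break-even ICC for 8.5 per 100.** Power at d = 0.085 is 80% when n_e = 538, that is Deff = 900 / 538 = 1.673. Then ICC = (1.673 / Deff_M − 1) / 59:
- Deff_M 1: 0.0114
- Deff_M 0.55: 0.035
- Deff_M 0.2: 0.125

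Other two-sided variance choices put the first of these between 0.010 and 0.0115. A one-sided test would move it to about 0.019.

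**Across the ICCs listed in Section 5.2, at Deff_M 1:**

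| ICC | Source | Deff | Detectable difference per 100 | Power at 8.5 |
|---|---|---|---|---|
| 0.0003 | maternal death | 1.018 | 6.6 | 95% |
| 0.005 | neonatal death | 1.295 | 7.5 | 89% |
| 0.01 | plan's value | 1.590 | 8.3 | 82% |
| 0.011 | maternal median | 1.649 | 8.4 | 81% |
| 0.013 | newborn lower quartile | 1.767 | 8.7 | 78% |
| 0.037 | maternal upper quartile | 3.183 | 11.7 | 53% |
| 0.054 | newborn median | 4.186 | 13.4 | 42% |
| 0.075 | newborn upper quartile | 5.425 | about 15 | 34% |

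**With a matching gain:**

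| Deff_M | ICC 0.01 | ICC 0.054 | ICC 0.075 |
|---|---|---|---|
| 0.55 | 6.2 (97%) | 10.0 (67%) | 11.3 (55%) |
| 0.2 | 3.7 (above 99%) | 6.0 (98%) | 6.9 (94%) |

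Entries are the detectable difference per 100, with power at 8.5 in brackets.

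**Large effects.** At ICC 0.075 and Deff_M 1, a 20-point difference from 50% has 96% power. The Karnataka pilot examples in Section 2.2 rose by 45 points (breastfeeding, 50% to 95%), 58 points (oxytocin, 8% to 66%) and 89 points (hand hygiene, 11% to 100%).

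**The case against.** The best defence is that the process-measure sentence states its own ICC, and a specific input overrides a general lead-in. The 0.075 is justified by newborn outcomes, and the paragraph that follows it concerns health outcomes only. The natural intention may therefore be 0.075 for health outcomes and 0.01, the study-wide value of Section 5.2, for process measures. That reading is plausible, but the text does not state it, and process measures are named just before 0.075 is introduced. Even if it is right, it does not make 0.01 a worst case, because Section 5.2 contains no process-measure ICC and claims less for 0.01.

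Three further points stand as limits on the size of the concern.
- Any detectable difference loses its 80% power just above the ICC it was planned on, so the break-even of 0.0114 mainly shows that the figure has little margin. That is ordinary for a planning value, though not for one described as most conservative.
- The powers of 34% to 53% apply ICCs for health outcomes to observed staff practice, and they fix the comparison rate at 50%, the least favourable rate. At the pilot baselines of 8% and 11%, the detectable increase at ICC 0.075 and Deff_M 1 is about 10.4 and 11.4 per 100, not 15.
- Matching may recover the loss. In the Mexico study cited in Section 5.2, 10 of 14 outcomes had Deff_M of 0.2 or smaller. At 0.2, 8.5 per 100 keeps 94% power even at ICC 0.075.

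**Conclusion.** The inconsistency is real. The section gives two ICCs without saying which outcomes each covers, and it presents 0.01 as the most conservative ICC when it is a mid-range planning value among those listed. The 8.5 per 100 is correct for its stated inputs and holds at 80% power up to an ICC of about 0.011 without a matching gain. At ICC 0.075 the comparable figure is about 15 per 100.

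These numbers rest on a two-sided 5% test, a 50% comparison rate, equal facility samples of 60, and ICCs borrowed from maternal and newborn outcomes. They show sensitivity, not an underpowered comparison. The effects the plan expects are well above 15 points, the test adjusts for clustering whatever ICC was planned, and the primary analysis is untouched. This is a low-priority correction of wording and of one stated figure.

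**What to change.** In Section 5.1, Secondary analyses:
- Say which outcomes the ICC of 0.075 applies to.
- In the process-measure calculation, remove the description of 0.01 as the most conservative ICC and state that no ICC for process measures was available.
- Replace the single 8.5 per 100 with a range at a 50% comparison rate. At Deff_M 1 this is about 8.3 at ICC 0.01, 13.4 at 0.054 and 15 at 0.075. At Deff_M 0.55 it is 6.2, 10.0 and 11.3. Label these as illustrative, since the ICCs come from other outcomes.
- Keep the statement that much larger differences are expected.

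The cost is two wording edits, one restated range, and a less favourable figure on paper. Sample size, test and data collection do not change.

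### The power claim for process measures on 15 matched pairs rests on an unstated large-sample reference, and its ICC of 0.01 conflicts with the 0.075 announced in the same section

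*Combined protocol and SAP*

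**What the plan says.** Section 5.1, Secondary analyses, gives the method as "Secondary analyses will use the Rao-Scott chi-square test, adjusted for matching and clustering" and adds that "all tests will be performed at a 5% type I error rate". It then introduces its power figures: "The following power calculations again assume an intracluster correlation of 0.075".

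The process-measure paragraph of the same section takes 15 matched pairs (30 facilities), 60 births per facility, 1,800 births in all, a comparison rate of 50%, Deff_M = 1 and an ICC of 0.01. It labels the last two as the most conservative values. On these inputs "the Rao-Scott chi-square test statistic will have greater than 80% power (with a 5% Type I error) to detect a minimum difference in rates" of 8.5 per 100. It adds that, from the pilot, "we expect to see much larger differences than 8.5 per 100".

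The interim uses the same test. Section 5.1 says "an interim Rao-Scott chi-square test will be performed after approximately 25% (45,000) of the total births are enrolled", and "In order to stop the study at this point in favor of the SCC program, the P-value for this Rao-Scott chi-square test must be" at most 0.001. Section 4.2 ties this monitoring to outcome data from the first 15 pairs (Phase II).

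Neither Section 5.1 nor the Statistical power part of Section 5.2 states a variance estimator, degrees of freedom, an F or t reference, or a permutation test.

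**The concern.** A chi-square reference treats the between-cluster variance as known. With 15 pairs it has to be estimated, and adjusting for matching suggests estimating it from the 15 pair contrasts, which gives 14 degrees of freedom. The usual 1.96 cut-off is then too low, and the stated power and the stated 5% level cannot both hold at the stated inputs.

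The same sentence has a second weakness. The section announces one ICC for its power calculations and the process-measure paragraph uses another that is 7.5 times smaller. At stake are the credibility of the 8.5 per 100 figure and, to a lesser degree, the level of the process-measure tests and of the interim test.

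**Working it through.** **Inputs** (Section 5.1 unless noted): 900 births per arm; m = 60; ICC 0.01; Deff_M = 1; 50% vs 58.5%; 5% level, taken as two-sided because the plan does not say. Section 5.2 gives Deff_C = 1 + (m-1) x ICC.

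**1. The plan's own figure.**
- Deff_C = 1 + 59 x 0.01 = 1.59; effective n per arm = 900/1.59 = 566.
- SE = sqrt((0.25 + 0.585 x 0.415)/566) = 0.0295; noncentrality = 0.085/0.0295 = 2.88.
- Normal power = P(Z > 1.96 - 2.88) = 82.1%. The claim of more than 80% reproduces, and the 80% detectable difference is 8.3 per 100.

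**2. Level if 1.96 is applied to an estimated variance.** Level = 2 x P(t_df > 1.96).
- Pair contrasts, 14 df: 7.0%.
- Variance pooled within arms, 28 df: 6.0%.
- Simulation of 200,000 null trials (15 pairs x 60 births, ICC 0.01, no pair correlation): 7.0% and 6.0%.
- Arm-based variance with a pair correlation of 0.45 in facility means (assumed, to match Deff_M 0.55): about 1.4%, which is conservative.

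**3. Power at 8.5 per 100** (noncentral t, noncentrality 2.88).

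| Variance | Power, 1.96 cut-off | Power, true 5% test | 80% detectable difference, true 5% test |
|---|---|---|---|
| Pair contrasts, 14 df | 81.5% (level 7.0%) | 76.4% (cut-off 2.14) | 8.9 per 100 |
| Pooled within arms, 28 df | 81.8% (level 6.0%) | 79.4% (cut-off 2.05) | 8.6 per 100 |

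Away from the worst case, F(1,14) power at 8.5 per 100 and ICC 0.01 is 95% at Deff_M 0.55, and 88% at a 20% comparison rate with Deff_M 1.

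**4. The ICC of 0.075.**
- Deff_C = 1 + 59 x 0.075 = 5.425; effective n = 900/5.425 = 166; SE = sqrt(0.4928/166) = 0.0545; noncentrality = 1.56.
- Power at 8.5 per 100: 34% (normal), 31% (F(1,14)). Detectable difference: 15.0 and 16.1 per 100.
- With Deff_M 0.55 as well: 5.425 x 0.55 = 2.98; noncentrality = 1.56/sqrt(0.55) = 2.10; power 56% (normal), 50% (F(1,14)).
- Cross-check on the health outcomes in the preceding paragraph: Deff_C = 1 + 1,439 x 0.075 = 108.9; 85,982/108.9 = 789 per arm; 2.80 x sqrt(0.5/789) = 7.0 per 100, and x sqrt(0.55) = 5.2. So 0.075 does underlie the 7 and 5 per 100 there, whereas 8.5 per 100 needs 0.01.

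**5. Interim at nominal two-sided 0.001** (cut-off 3.29).
- 15 pairs: 30 x 1,440 = 43,200 births, close to the 45,000 trigger. 2 x P(t14 > 3.29) = 0.54%; 0.27% with 28 df.
- All 60 pairs contributing: 2 x P(t59 > 3.29) = 0.17%.
- Overall two-sided error with a pair-based variance (simulated): about 5.85% with a 15-pair interim, 5.56% if all 60 pairs contribute. The final test alone gives 5.5%, so most of the excess is not from the interim.

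**The case against.** **This is an omission in a section that asks for a brief description.** The plan never prints 1.96 or 14 df, and an F or t reference may be intended. That is fair as to the level, which would then be correct. It does not save the power sentence: with an F reference the figure is 76% on pair contrasts or 79% pooled within arms, both below the stated 80%.

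**The level error has no fixed direction.** This stands. A reader might infer that every process measure would be tested at 7%. The documents do not support that, because the variance estimator is unstated and an arm-based variance with effective matching would be conservative.

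**The two faults are alternatives.** This also stands. A reader might put 7.0% and 76% together as joint failings. The 1.96 cut-off on pair variance keeps 81.5% power, and the 76% belongs to a test whose level is correct.

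**The shortfall is confined to a corner.** Largely true. It needs Deff_M of 1, a 50% comparison rate and a difference near 8.5. Section 5.2 reports Deff_M of at most 0.55 in the Mexico trial, and the pilot changes in Section 2.2 were far larger. It would be wrong to conclude that the process measures are underpowered for the effects the plan expects.

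**The 0.075 may be meant only for health outcomes.** The cross-check supports that as a description of what was calculated. But the sentence announces the power calculations that follow without limiting them, the process paragraph calls 0.01 most conservative, and the ICC sources in Section 5.2 concern health outcomes, not process measures.

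**The interim point is conditional.** Agreed. Section 5.1 triggers on births, and the Section 4.2 milestones date the interim at month 40, when all facilities are due to be enrolled. The stopping rule is a guideline, so crossing it is not stopping. A reader might infer serious inflation of the trial's error from the 15-pair figure; the overall effect is about 0.3 to 0.4 points.

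**Conclusion.** The point holds as a minor one. The claim of more than 80% power at a 5% level for 8.5 per 100 is true only under a large-sample reference. With the variance estimated from 15 pairs, the choice is about 81.5% power at a 7.0% level, or about 76% power at a true 5% level. Pooling within arms narrows the gap to a 6.0% level or 79.4% power. These figures assume two-sided tests, equal cluster sizes and the plan's own worst-case inputs. The practical effect is small: the detectable difference moves from 8.5 to about 8.9 per 100.

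The ICC conflict is the more consequential part of the same statement. It moves power at 8.5 per 100 from 82% to about 31-34%, and the detectable difference to about 15-16 per 100, still at Deff_M 1. The documents do not settle which value applies to process measures.

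For the interim, the two-sided level is about 0.54% instead of 0.1% if only the 15 Phase II pairs enter with a pair-based variance. The consequence for overall error is modest.

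**What to change.** - State that the Rao-Scott statistic takes the pair as the sampling unit and is referred to F(1, pairs-1), or use the equivalent paired t or permutation test on pair contrasts. For 15 pairs the cut-offs are |t| of 2.14 at 5% and 4.14 at P = 0.001; for 60 pairs at the final, 2.00. A permutation test on 15 pairs can reach the interim threshold, since its smallest two-sided P is 2/2^15 = 0.00006.
- State which pairs enter the interim, and align Section 5.1 with Section 4.2 and its milestone table.
- Reconcile the two ICCs in Section 5.1, give the basis for the process-measure value, and remove the most-conservative label if 0.01 is kept alongside 0.075.
- Restate the process-measure detectable difference on 14 df: about 8.9 per 100 at ICC 0.01, about 16 per 100 at ICC 0.075.

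The change is SAP wording. It costs about one point of final-test power on the plan's own inputs (86,000 per arm, 60 vs 51 per 1,000, Deff_C 15.4, Deff_M 0.55: noncentrality 2.80 on 59 df, 79.9% at 1.96 and 78.7% at 2.00), and a slightly less favourable stated figure for the process measures.
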